9.7.1.3 Intent-to-Treat Population

The Intent-to-Treat (ITT) Population will consist of all patients in the Safety Population who had at least 1 postbaseline assessment of the MADRS total score during the OLTP of the study.

9.7.2 Patient Disposition

The number and percentage of patients in the 3 analysis populations will be summarized overall by study center.

For *de novo* enrolled patients, screen failures (ie, patients who were screened but not included in the Safety Population) and the associated reasons for failure to enroll will be tabulated overall for the Screened Population.

The number and percentage of patients who complete the OLTP, who prematurely discontinue from the OLTP, and who complete the safety follow-up period will be summarized overall and by reasons for premature discontinuation for the Safety Population.

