- To evaluate the psychotomimetic effects of rapastinel (450 mg IV weekly or once every 2 weeks) as an adjunct to ongoing ADT, as measured by the change from baseline in BPRS+ at all postdose evaluations
- To evaluate the dissociative effects of rapastinel (450 mg IV weekly or once every 2 weeks) as an adjunct to ongoing ADT, as measured by the change from baseline in CADSS at all postdose evaluations

9.0 **INVESTIGATIONAL PLAN**

9.1 **OVERALL STUDY DESIGN AND PLAN: DESCRIPTION**

[figure not shown]
Study RAP-MD-06 is a multicenter, open-label study to evaluate the long-term safety and tolerability of rapastinel as adjunctive therapy to ADT in adult patients with MDD who either completed the RAP-MD-04 Double-blind Treatment Period (DBTP) at Visit 122 (Week 104, ET) or who do not meet criteria to be randomized into the DBTP of RAP-MD-04 and are therefore discontinued from that study. The enrollment of patients who did not participate in RAP-MD-04 (identified as *de novo* enrollment patients) may be considered at some study centers if enrollment of rollover patients does not meet targeted projections and will not be allowed unless specified in an official communication from the Sponsor.

The study will be conducted in the following periods:

- Up to 2-week screening period
- Up to 52-week OLTP
- 2-week safety follow-up period

The study is planned to be terminated when 100 patients have completed the 52-week OLTP. The actual sample size is expected to be larger than 100 patients and some patients will have less than 52 weeks of open-label treatment (as many as 500 patients are expected to enter the OLTP of Study RAP-MD-06).

[Figure 9.1-1](#) provides the study design schematic. The schedule of evaluations is presented in [Section 2.0](#), and detailed descriptions of the procedures conducted at each study visit can be found in [Section 9.5](#).

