9.1.2 Open-label Treatment Period

Approximately 500 patients are planned for enrollment in the OLTP; all patients will receive open-label rapastinel at 450 mg IV (adjunctive to ADT), either weekly or once every 2 weeks, based upon the Investigator's discretion. Patients will skip odd-numbered visits if being treated on a biweekly basis). The once-every-2-weeks schedule can only be initiated on even-numbered visits in order to maintain the appropriate visit schedule. Patients who are on a once-every-2-weeks schedule can be transitioned back to weekly visits at any visit.

Upon completion of the OLTP at Visit 54 (Week 52, ET), patients will enter a 2-week safety follow-up period and will return to the clinic at Visit 55 (Week 54). The maximum duration of the study will be 56 weeks.

The study will be terminated when 100 patients have completed the 52-week OLTP.

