9.3.2 Exclusion Criteria

Note: For rollover patients who completed the lead-in study (RAP-MD-04), medical, psychiatric, and medication histories from Visit 1 of the lead-in study will be used (Exclusion Criteria Nos. 1-8, 12-14, 17, 21-25, and 27). Because Visit 1 clinical laboratory or ECG results will not be available on the day of Visit 1, if there are any safety concerns related to Visit 1 clinical laboratory or ECG results, patients can be discontinued at Visit 2.

Patients who meet any of the following criteria will not be eligible to participate in the study:

Exclusion criteria to be assessed at Screening (Visit 1)

Psychiatric and Treatment-Related Criteria:

1. DSM-5-based diagnosis of any disorder other than MDD that was the primary focus of treatment within 6 months before Visit 1. Comorbid generalized anxiety disorder, social anxiety disorder, or specific phobias are acceptable provided they play a secondary role in the balance of symptoms and are not the primary driver of treatment decisions.
2. Lifetime history of meeting DSM-5 criteria for:
 - Schizophrenia spectrum or other psychotic disorder
 - Bipolar or related disorder
 - Major neurocognitive disorder
 - Neurodevelopmental disorder of greater than mild severity or of a severity that impacts the patient's ability to consent, follow study directions, or otherwise safely participate in the study
 - Dissociative disorder

- Screen failure (failure to meet inclusion/exclusion criteria)
- Pregnancy
- Withdrawal of consent
- AE
- Lack of efficacy
- Protocol violation
- Noncompliance with IP
- Noncompliance with ADT
- Lost to follow-up
- Study terminated by Sponsor
- Study center terminated by Sponsor
- Other

All patients who prematurely discontinue from the study, regardless of cause, should be seen for a final assessment at an ET Visit. A *final assessment* will be defined as completion of the evaluations scheduled for all patients at Visit 54 (Week 52). All patients discontinuing the study prematurely should enter the 2-week safety follow-up period.

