9.7.9 Determination of Sample Size

Approximately 500 patients are expected to enter the OLTP. The study will be terminated when 100 patients have completed the 52-week OLTP.

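### A planned stop at 100 completers makes the completion percentage track the number entered, and crude discontinuation percentages understate 52-week risk

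*Protocol*

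**What the plan says.** - **Stopping rule.** Section 9.7.9: "The study will be terminated when 100 patients have completed the 52-week OLTP". Sections 9.1 and 9.1.2 and the synopsis say the same.
- **Number entering.** Section 9.7.9: "Approximately 500 patients are expected to enter the OLTP". Section 9.1 words the same number as an upper figure and accepts truncation: "some patients will have less than 52 weeks of open-label treatment (as many as 500 patients are expected to enter the OLTP".
- **Completion.** Section 9.1.2 places it at Week 52: "Upon completion of the OLTP at Visit 54 (Week 52, ET), patients will enter a 2-week safety follow-up period".
- **Disposition.** Section 9.7.2 summarizes "The number and percentage of patients who complete the OLTP, who prematurely discontinue from the OLTP, and who complete the safety follow-up period", overall and by reason for premature discontinuation, on the Safety Population. Section 9.7.1.2 defines that population as everyone with at least one open-label dose, whatever follow-up was possible.
- **Reasons.** The list of discontinuation reasons, printed just before Section 9.3.4, has "Study terminated by Sponsor" as an entry of its own beside AE and lack of efficacy.
- **AE discontinuation.** Section 9.7.6.1 reports the incidence of AEs leading to discontinuation of IP by preferred term. Section 9.7.4.1 summarizes exposure by duration only.

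**The concern.** A patient still on treatment when the 100th completer finishes has not dropped out. That patient's follow-up is administratively censored. Section 9.7.2 has only two outcomes for the open-label period, and such a patient has not completed it, so the other category is the only one left.

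Two separate consequences follow.

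1. The stopping rule fixes the numerator of the completion percentage at about 100. The percentage then depends on how many patients entered, not on how well treatment was tolerated.
2. The AE and lack-of-efficacy percentages divide by all treated patients, including those who never had 52 weeks available. They count fewer events than full follow-up would have shown.

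Long-term safety and tolerability is the study's sole objective, and the study is meant to support a regulatory application (Sections 7.0 and 8.0). Retention and discontinuation for AEs are central tolerability results, and readers will naturally take them as 52-week figures.

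**Working it through.** **Inputs from the protocol.** Stop at 100 completers; about 500 entering (9.7.9); completion at Week 52 (9.1.2); denominator is the Safety Population (9.7.2).

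**Inputs that are assumed.** The protocol gives no accrual, drop-out or AE-discontinuation rate. I take uniform accrual over A = 26, 52 or 70 weeks, a constant drop-out hazard with 52-week risk D = 20%, 30% or 40%, and an AE share of drop-out that makes the 52-week AE-discontinuation risk 10%.

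**Step 1: completion on the plan's own numbers.** The protocol states no completion percentage; the figures imply one.
- 500 enter: 100/500 = 20% complete, and 400 (80%) do not.
- 400 enter: 100/400 = 25%.
- 300 enter: 100/300 = 33.3%.

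No drop-out rate appears in these sums. The 80% mixes true drop-outs with patients cut off.

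**Step 2: effect on crude drop-out.** Let S = 1 − D and h = −ln(S)/52. Patients entering at least 52 weeks before the stop time T number 500(T − 52)/A, and a fraction S of them complete. Setting 500·S·(T − 52)/A = 100 gives T = 52 + 0.2A/S. A patient entering at time e has potential follow-up f = min(52, T − e). Crude drop-out is the mean of 1 − exp(−hf). The share cut off is the sum of exp(−hf) over patients with f < 52, divided by all entrants.

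Example, D = 40% and A = 52:
- S = 0.6; h = 0.5108/52 = 0.00982; T = 52 + 0.2 × 52/0.6 = 69.3 weeks.
- Full 52 weeks available: 17.33/52 = one third, or 166.7 patients, of whom 60% = 100 complete.
- For the other two thirds, f runs evenly from 17.3 to 52 weeks. Mean probability of still being on treatment: (0.843 − 0.600)/(0.00982 × 34.67) = 0.715.
- Cut off by the stop: 2/3 × 0.715 = 47.7%, about 238 patients.
- Own drop-out shown: 100 − 20 − 47.7 = 32.3%, against a 52-week risk of 40% (ratio 0.81).
- With AEs a quarter of drop-out: 32.3/4 = 8.1% shown, against 10%.

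All scenarios:

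| 52-week drop-out | Accrual (weeks) | Cut off by stop | 10% AE risk shows as |
|---|---|---|---|
| 20% | 26 | 313 | 8.7% |
| 20% | 52 | 327 | 7.3% |
| 20% | 70 | 333 | 6.4% |
| 30% | 26 | 267 | 8.9% |
| 30% | 52 | 285 | 7.7% |
| 30% | 70 | 298 | 6.8% |
| 40% | 26 | 218 | 9.1% |
| 40% | 52 | 238 | 8.1% |
| 40% | 70 | 254 | 7.3% |

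In the third row the stop falls at 69.5 weeks, when about 496 have entered. On a wider range (D from 20% to 60%, accrual from 26 weeks up to the longest that lets 500 enter), crude drop-out is 0.64 to 0.96 times the 52-week risk, and about 22% to 67% of the 500 are cut off.

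**Step 3: what relabelling does.** The AE percentage is AE drop-outs divided by the Safety Population. In the example, that is about 40 of 500, or 8.1%. Moving 238 patients from premature discontinuation to a separate category changes neither term, so the figure stays at 8.1%. Only a measure that accounts for follow-up brings it to 10%.

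**Step 4: completion among those with 52 weeks available.** In the example, 100/166.7 = 60% = 1 − 0.40. This returns the assumed risk, as it must. It shows that the measure has the right target and says nothing about this trial's retention.

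**The case against.** The strongest case against is that the table is broken down by reason and Sponsor termination has its own line. If cut-off patients are coded there, a reader sees how much non-completion is administrative. Section 9.1 openly says that "some patients will have less than 52 weeks of open-label treatment", exposure duration is summarized, the study is descriptive, and no passage claims to estimate a 52-week cumulative risk. A crude proportion of treated patients is correct as that. Much of this stands, and it rules out four stronger readings that a reader might infer:

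- **AE and efficacy drop-outs are mixed with cut-off patients.** The separate reason line prevents that.
- **Completion is fixed at 20% by design.** Only the numerator is fixed. The 500 is an expectation, and de novo enrolment depends on a Sponsor decision.
- **The labelling causes the understated AE percentage.** Step 3 shows that it does not; truncated follow-up does.
- **The protocol expressly classes cut-off patients as premature discontinuations.** It does not say so. The coding is a strong inference from the two categories and the list of reasons, whose lead-in is not in the available text.

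It can also be said that time-to-event displays belong in the SAP. A protocol may leave them there. Here, though, it specifies a crude two-category method for a design that plans truncation, and that method suits the design poorly. Adding to it is a change to what is written, not a complaint about missing detail.

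**Conclusion.** The point holds in a limited form and is worth acting on. If cut-off patients are coded as Sponsor terminations within premature discontinuation, completion will be about 20% with 500 entrants, 25% with 400 and 33% with 300, and will not measure retention. The crude AE and lack-of-efficacy percentages are right as crude incidence but lie below the 52-week risk whenever patients are cut off before Week 52.

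That direction needs no accrual figure; the size does. Under uniform accrual over 26 to 70 weeks, constant hazards and 20% to 40% drop-out, 218 to 333 patients are cut off and a 10% AE-discontinuation risk shows as 6.4% to 9.1%, a shortfall of 0.9 to 3.6 percentage points. The shortfall shrinks as true drop-out rises or accrual shortens. None of these rates can be derived from the protocol.

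**What to change.** In Section 9.7.2:

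1. Keep the crude table, but show patients ongoing at the planned stop on a separate line outside premature discontinuation. This corrects the completion and discontinuation labels only.
2. Add a descriptive cumulative incidence of discontinuation over 52 weeks, overall, for AE and for lack of efficacy, censored at the planned stop. For the single reasons, treat discontinuation for other reasons as a competing event. This corrects the understated rates.
3. Report completion also among patients who entered at least 52 weeks before the stop.
4. Label the AE-discontinuation percentages in Section 9.7.6.1 as crude incidence and refer to the summary in item 2.

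Items 2 and 3 assume that discontinuation risk does not depend on when a patient entered. If rollover and de novo patients enter at different times, show the curves for each group.

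The cost is one extra descriptive table from first-dose, last-dose and termination data already collected. The stopping rule, study conduct and the descriptive nature of the analysis do not change.

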9.7.3 Demographics and Other Baseline Characteristics

Demographic parameters (eg, age, race, ethnicity, sex, weight, height, body mass index) and other baseline characteristics will be summarized overall for the Safety Population and the ITT Population.

9.7.4 Extent of Exposure and Treatment Compliance

9.7.4.1 Extent of Exposure

Exposure to rapastinel for the Safety Population during the OLTP will be summarized for treatment duration, calculated as the number of days from the date of the first dose of open-label rapastinel taken to the date of the last dose taken during the OLTP, inclusive. Descriptive statistics (number of patients, mean, SD, minimum, median, and maximum) will be presented.

Prior medication will be defined as any medication started before the date of first dose of IP in the first lead-in study for rollover patients or any medication started before the date of the first dose of open-label IP in this study for *de novo* patients. *Concomitant medication* during the OLTP will be defined as any medication taken on or after the date of the first dose of open-label IP during the OLTP.

The use of prior medication will be summarized by the number and percentage of patients receiving each medication within each therapeutic class for the Safety Population. The use of concomitant medications during the OLTP will be summarized by the number and percentage of patients receiving each medication within each therapeutic class for the Safety Population. Multiple use of the same medication by a patient will only be counted once.

The number and percentage of patients taking each qualifying ADT in the OLTP will be summarized for the Safety Population. Mean daily dose and duration of treatment with each qualifying ADT will be summarized using descriptive statistics (number of patients, mean, SD, median, minimum, and maximum) for the Safety Population.

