The mechanism of action of rapastinel is entirely different from that of atypical antipsychotics. Rapastinel is an N-methyl-D-aspartate receptor (NMDAR) modulator with a novel and complex pharmacological mechanism of action, acting as a nonselective agent at NR2 subunits and displaying properties as a functional partial agonist in a number of pharmacological assays.

Rapastinel has demonstrated antidepressant properties in relevant animal models, displays cognitive enhancing properties in treated animals, and facilitates hippocampal long-term potentiation of synaptic transmission in preclinical models. In contrast to ketamine, no signal of abuse liability was detected in informative animal models.

Rapastinel is available as an intravenous (IV) formulation only. In two Phase 2 clinical studies in patients with MDD, single IV doses of rapastinel 5 mg/kg and 10 mg/kg have been shown to produce marked antidepressant effects within 1 day that lasted for approximately 1 week or longer in responding patients. These antidepressant effects are very similar to ketamine's effects when administered at a low dose as an infusion. In a systematic review and meta-analysis of ketamine and other NMDAR antagonists in the treatment of major depression, a single infusion of ketamine produced a rapid, yet transient antidepressant effect, accompanied by brief psychotomimetic and dissociative effects ([Newport et al, 2015](#)).

The available Phase 1 and 2 data demonstrated a favorable safety and tolerability profile of rapastinel. In contrast to ketamine, rapastinel has not shown a high likelihood to induce psychotomimetic or dissociative effects in humans so far.

The purpose of this study is to assess the safety and tolerability of rapastinel when administered open-label as an adjunctive treatment at a dose of 450 mg as a short IV infusion in patients with MDD. The study is intended to support an application for regulatory approval of rapastinel as adjunctive treatment for MDD.

8.0 **STUDY OBJECTIVES**

The objective of this study is to evaluate the long-term safety and tolerability of rapastinel as adjunctive to ADT in patients with MDD.

Safety Objectives

- To evaluate the safety and tolerability of rapastinel (450 mg IV weekly or once every 2 weeks [biweekly]) as an adjunct to ongoing ADT, as evaluated by AEs, clinical laboratory measures, ECGs, vital signs, [REDACTED]

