9.4.6 Selection of Dosages in the Study

A rapastinel dose of 450 mg was chosen for this study based on results from 2 Phase 2 clinical studies of patients with MDD in which single IV doses of rapastinel 5 mg/kg and 10 mg/kg were shown to produce marked antidepressant effects within 1 day that lasted approximately 1 week or longer in responding patients. The 450-mg IV dose is expected to provide an appropriate dose for most patients based upon the Phase 2 study results. The use of a single-unit dose is intended to aid in the simplicity of administration and avoid dosing errors.

RAP-MD-04 also assessed both weekly and biweekly dosing regimens. While the GLYX13-C-202 study also assessed the effect of weekly and biweekly administration after initial stabilization, and found no differences, the comparison was only carried out for 6 weeks in that study. Assessing a less frequent dosing regimen over the more substantial time period of 26 weeks to 2 years in RAP-MD-04 followed by an additional 52 weeks of treatment in RAP-MD-06 is expected to yield a better understanding of the long-term safety characteristics of rapastinel treatment and allow proper guidance to physicians regarding treatment beyond initial stabilization.

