9.7.4.2 Measurement of Treatment Compliance

Dosing compliance for a specified period is defined as the total number of IV doses actually taken by a patient during that period divided by the number of IV doses that were expected to be taken during the same period multiplied by 100. Descriptive statistics for IP compliance will be presented for each week, as well as for the whole OLTP for the Safety Population.

Dosing compliance for the background ADT during a specified period is defined as the doses actually taken by a patient during that period divided by the dose expected to be taken during the same period multiplied by 100. Descriptive statistics for ADT compliance during the OLTP will be presented for each ADT for the Safety Population.

[REDACTED]

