A TEAE occurring during the OLTP will be considered a newly emergent AE (NEAE) if the AE was not present before the first dose of open-label IP or was present before the first dose of open-label IP but increased in severity during the OLTP. The number and percentage of patients reporting NEAEs during the OLTP will be summarized by SOC and preferred term.

The number and percentage of patients reporting TEAEs will be tabulated by SOC and preferred term and further categorized by severity and causal relationship to the IP. If more than 1 AE is coded to the same preferred term for the same patient, the patient will be counted only once for that preferred term using the greatest severity and strictest causality for the summarization by severity and causal relationship.

The distribution of TEAEs by severity and relationship to the IP will be summarized.

An AE that occurs more than 30 days after the date of the last dose of IP will not be summarized.

The incidence of common ($\geq 2\%$ of patients) TEAEs and AEs leading to premature discontinuation of IP will be summarized by preferred term and will be sorted by decreasing frequency.

An SAE that occurred between the date of the first dose of the open-label IP and 30 days after the date of the last dose of IP, inclusive, will be considered an on-therapy SAE.

The number and percentage of patients who have on-therapy SAEs will be summarized by preferred term. In addition, the incidence of on-therapy SAEs that led to death will be summarized separately by preferred term.

The incidence of AEs leading to premature discontinuation of IP during the OLTP will be summarized by preferred term and will be sorted by decreasing frequency.

Listings will be presented for all patients with SAEs, patients with AEs leading to discontinuation, and patients who die (if any). All patients with SAEs, including SAEs reported during the screening period and the safety follow-up period, and patients discontinuing because of AEs occurring before the start of IP will be included in these listings.

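### AE percentages are not related to time at risk although follow-up is unequal by design, and rapastinel exposure is stated in days without dose counts

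*Protocol*

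**What the plan says.** **Adverse events.** Section 9.7.6.1: "The number and percentage of patients reporting TEAEs will be tabulated by SOC and preferred term". Newly emergent AEs and on-therapy SAEs are also given as numbers and percentages of patients, and AEs leading to discontinuation as incidence. A further table lists TEAEs seen in at least 2% of patients. An AE more than 30 days after the last dose is not counted. No patient-time denominator is stated.

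**Follow-up.** Section 9.7.9: "The study will be terminated when 100 patients have completed the 52-week OLTP", with about 500 patients expected to enter. Section 9.1 accepts that "some patients will have less than 52 weeks of open-label treatment".

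**Exposure.** Section 9.7.4.1 summarises rapastinel exposure as a length of time: "calculated as the number of days from the date of the first dose of open-label rapastinel taken to the date of the last dose", counted inclusively and described by n, mean, SD, minimum, median and maximum. For each background ADT the same section plans both mean daily dose and duration.

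**Compliance.** Section 9.7.4.2 defines it as "the total number of IV doses actually taken by a patient during that period divided by the number of IV doses that were expected", times 100, by week and for the whole open-label treatment period (OLTP).

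**Schedule.** Each dose is 450 mg, weekly or every 2 weeks at the investigator's discretion, with switching allowed (Sections 9.1.2 and 9.4.7). Section 8.0 names both schedules in the safety objectives. Section 9.4.6 says that assessing the less frequent regimen across RAP-MD-04 and this study "is expected to yield a better understanding of the long-term safety characteristics of rapastinel treatment and allow proper guidance to physicians".

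**The concern.** AE incidence and extent of exposure are the main products of an uncontrolled long-term safety study. Under this stopping rule up to 400 of about 500 patients may contribute less than 52 weeks, perhaps much less. A crude percentage then pools patients observed for a few weeks with patients observed for a year, and its value depends on how fast enrolment ran and when the study closed as well as on the drug. A reader of a study described as 52 weeks long may take the percentage as a one-year figure, which would usually be too low.

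On exposure, a patient dosed weekly and one dosed every 2 weeks can have almost the same treatment duration and the same compliance while receiving very different amounts of drug. The background ADT gets both dose and duration, whereas the investigational drug gets duration only.

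**Working it through.** The 500 and the 100 come without a power or precision calculation, so there is no derived figure to reproduce. The two checks below use the visit schedule and a labelled illustration.

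**1. Doses and days**

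Inputs: Visit 53 is Week 51 (Section 9.4.7.2), so visit *v* is Week *v* − 2. Biweekly patients skip odd-numbered visits (Sections 9.1.2, 9.4 and 9.4.7). Days = last dose date − first dose date + 1.

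Fully dosed completers, Visits 2 to 53:

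- Weekly: 52 doses; 52 × 450 mg = 23.4 g; 51 × 7 + 1 = 358 days.
- Biweekly: 26 doses, last at Week 50; 26 × 450 mg = 11.7 g; 50 × 7 + 1 = 351 days.

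Doses differ by a factor of 2 and days by 2% (358/351 = 1.02). Patients who switch fall between 26 and 52 doses within the same 351 to 358 days. Counting the Visit 1 dose of rollover patients gives 53 doses in 365 days against 27 in 358, which leaves the contrast as it was.

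For early stoppers the days can be identical. With a last dose at Week 12, 13 and 7 doses both give 12 × 7 + 1 = 85 days. With a last dose at Week 24, 25 and 13 doses both give 24 × 7 + 1 = 169 days.

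Compliance does not separate the schedules if expected doses follow the schedule in use: 52/52 = 26/26 = 100%. Section 9.4.7.2, taken literally, has all eligible patients dosed at Visits 2 through 53. On that reading the fully dosed biweekly patient scores 26/52 = 50%.

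**2. Crude percentage against one-year risk**

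From the protocol: 100 completers and 500 − 100 = 400 others. Assumed: a constant event rate *r* per patient-year, and a common follow-up *t* for the 400 of 0.25, 0.50 or 0.75 years (13, 26 or 39 weeks). The protocol gives neither.

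- Crude % = 100 × [0.2(1 − e^(−r)) + 0.8(1 − e^(−rt))]
- One-year risk % = 100 × (1 − e^(−r))

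For *r* = 0.20 and *t* = 0.25: 0.2 × 0.1813 + 0.8 × 0.0488 = 0.0753, or 7.5%.

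| Rate per patient-year | One-year risk | Crude, 13 wk | Crude, 26 wk | Crude, 39 wk |
|---|---|---|---|---|
| 0.05 | 4.9% | 2.0% | 3.0% | 3.9% |
| 0.20 | 18.1% | 7.5% | 11.2% | 14.8% |
| 0.50 | 39.3% | 17.3% | 25.6% | 32.9% |

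Adding the 30-day window for everyone at 0.20 gives 9.0%, 12.7% and 16.2%.

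**3. What a first-event rate would show**

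At *r* = 0.20 the expected number of patients with an event is 37.6, 56.2 or 73.8, over 188, 281 or 369 patient-years to first event. Each ratio is 0.20. Under these assumptions the rate does not move with follow-up, while the crude percentage roughly doubles.

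**The case against.** The strongest reply is that this is ordinary SAP content. Dose counts, patient-years and exposure-adjusted rates are routine tables, and the SAP is not available here. Nothing in Section 9.7.4.1 says duration will be the sole exposure table, and the absence of a reference to the SAP does not make a section exhaustive. That stands as a limit: the point concerns the measures the protocol states and does not show that the analyses will be missing. It does not remove the point, because the stated measure is a poor match to a stopping rule in the same document.

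Four stronger readings are tempting, and the text does not support them.

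- *Time at risk is not shown at all.* The duration summary gives n and mean, and n × mean is total patient-days on treatment. What is missing is the link between AEs and that time, the 30-day tail, and time to first event.
- *Less frequent events disappear below the 2% cut-off.* The full table by SOC and preferred term has no cut-off, and SAEs, deaths and discontinuations are summarised separately.
- *The protocol promises an analysis by schedule and omits it.* Section 8.0 names the schedules together and Section 9.4.6 speaks of RAP-MD-04 followed by this study. No split is promised, and one would be confounded by investigator choice and switching.
- *The percentages are wrong.* They are valid descriptions of what was observed, and the protocol never calls them 52-week risks.

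Two further replies stand in part. If events cluster early, the gap in the illustration shrinks. Weekly compliance tables may hint at how many patients were due a dose in a given week, but only on one reading of expected doses, and they do not give doses per patient.

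**Conclusion.** The point holds as a cheap improvement; it is not an error in a stated number. AE percentages are the only AE measure Section 9.7.6.1 states, and the stopping rule makes the follow-up behind them unequal. Read as long-term risk they would understate 52-week incidence. The size depends on unknown follow-up: in the 0.20 per patient-year illustration, 7.5% to 14.8% against 18.1%, assuming a constant hazard and equal follow-up among the 400. On exposure, the stated summaries leave an up to twofold difference in doses invisible at full adherence, which follows from the schedule alone.

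**What to change.** Keep the duration definition and the percentages.

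- **Section 9.7.6.1:** add first-event rates per patient-year beside the percentages, as patients with a first event divided by time at risk. Run time at risk from the first open-label dose to the earliest of first event, end of observation, or 30 days after the last dose. For all AEs, take the final visit as end of observation, because Section 9.5.2.1.4 afterwards sends only SAEs and potentially related AEs to the eCRF. For completers that visit (Week 54) is 21 days after a Week 51 dose or 28 days after a Week 50 dose, inside the 30-day window.
- **Section 9.7.4.1:** add number of doses received and total patient-years.
- **Optional:** dose counts and patient-time by schedule received, labelled descriptive and non-randomised.

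Separately, reconcile Section 9.4.7.2 with Sections 9.1.2, 9.4 and 9.4.7, so that expected doses have one meaning in the compliance ratio.

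The cost is two or three sentences and a few descriptive tables, from injection dates and times already captured under Section 9.4.12. The downside is that patient-year rates assume a roughly constant hazard, so they should be presented descriptively and should not replace the percentages.
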